2.8.2 Statistical hypothesis, model, and method of analysis

Statistical methodologies for efficacy variables are detailed in Table 2.8.2-1 (Primary efficacy), Table 2.8.2-2 (Secondary efficacy) and Table 2.8.2-3 (Exploratory efficacy).

Table 2.8.2-1 Primary and Key Secondary Efficacy Analyses

Study Endpoint	Method of Analysis
Mean change in BCVA from baseline to months 12 and 24	1. Mixed Modelling (Refer to Section 2.8.2.5) 2. Summary statistics of change from baseline will be presented.
Mean change in central retinal thickness (CRT) from baseline to months 12 and 24	1. Mixed Modelling (Refer to Section 2.8.2.5) 2. Summary statistics of change from baseline will be presented.
Mean number of injections from baseline to months 12 and 24	1. Binomial Model 2. All data will be listed.

Table 2.8.2-2 Additional Secondary Efficacy Analyses

Study Endpoint	Method of Analysis
Geographic Atrophy from Baseline to Month 12 / 24 (newly developed geographic atrophy between baseline and Month 24 (Yes/No))	1. Logistic regression model (Refer to Section 2.8.2.8) 2. Survival Analysis (Refer to Section 2.8.2.10)
Geographic Atrophy from Baseline to Month 12 / 24 (Change in area of geographic atrophy from the visit where geographic atrophy was first present)	1. Mixed Modelling (Refer to Section 2.8.2.8)
Proportion of patients showing greater than or equal to 15 letters (EDTRS) gain from baseline to month 24	1. Logistic regression model (Refer to Section 2.8.2.8)
Proportion of patients showing less than 15 letters loss from baseline to month 24	1. Logistic regression model (Refer to Section 2.8.2.8)
Proportion of patients showing no IRF and SRF at month 2, 12 and 24	1. Logistic regression model (Refer to Section 2.8.2.8)

Table 2.8.2-3 Exploratory Efficacy Analyses

Study Endpoint	Method of Analysis
Proportion of patients with SRF, as assessed by the █████ CRC, and IRF, as assessed by investigators at Baseline, who do not resolve their SRF and IRF by Month 24	1. Logistic regression model (Refer to Section 2.8.2.8)
The proportion of patients with a) SRF b) IRF c) both SRF and IRF d) neither SRF or IRF at baseline, 2, 12, 24 months	1. Logistic regression model (Refer to Section 2.8.2.8)

Proportion of patients with SRF at baseline who never resolve their SRF at any visit up to Month 2, 12 and 24 (irrespective of their IRF)	1. Logistic regression model (Refer to Section 2.8.2.8)
Proportion of patients with IRF at baseline who never resolve their IRF at any visit up to Month 2, 12 and 24 (irrespective of SRF)	1. Logistic regression model (Refer to Section 2.8.2.8)
Proportion of patients with IRF and SRF at baseline who never resolve either their IRF or SRF at any visit up to Month 2, 12 and 24.	1. Logistic regression model (Refer to Section 2.8.2.8)
Proportion of patients who show $\geq 6/12$ visual acuity at baseline, month 12 and 24	1. Logistic regression model (Refer to Section 2.8.2.8)
Proportion of patients who show 6/60 or worse visual acuity at baseline, month 12 and 24	1. Logistic regression model (Refer to Section 2.8.2.8)
Time to Breakpoint	1. Kaplan Meier Survival Analysis (Refer to Section 2.8.2.10)

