2.4.1.1 Baseline

Baseline is defined as the last available non-missing value collected just prior to the start of treatment in the study eye. Where a patient parameter value is missing for Visit 2:

1. If the patient has entered the treatment period (i.e. received at least one treatment), the baseline value for that patient will be imputed with the patient's Screening value.

2. If the patient never entered the treatment period, the baseline value will not be imputed.

Furthermore, patients with screening assessments, who do not enter the treatment period data, will only be included in data listings.

Note: Photography and FA performed no more than 14 days before the Baseline Visit will be accepted as the baseline examination (will not need to be repeated unless clinically indicated).

Note: BCVA performed no more than 2 days before the Baseline Visit will be accepted as the baseline examination. In addition, only BCVA data collected as per protocol (e.g. refracted ETDRS) will be accepted as the baseline examination.

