2.4.1.2 Post-baseline

All assessments obtained after the date of first dose of study drug are considered as post-baseline unless otherwise specified. Missing data for post-baseline values, for example due to discontinuation, loss to follow-up, or other types of censoring (e.g. due to rescue medication), will not be imputed. Only subjects with measurements at any given time point will be included in the analysis for that given parameter and visit. Refer to Section 2.4.3 for further details regarding the handling of missing dates.

The study day for a baseline or post-baseline scheduled or unscheduled visit is defined as:

$$\text{Study day} = (\text{Date of visit}) - (\text{date of first treatment}) + 1$$

The study day for a scheduled or unscheduled visit before baseline is defined as:

$$\text{Study day} = (\text{Date of visit}) - (\text{date of first treatment})$$

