2.8.1 Variables

The primary efficacy variable and key secondary variables are:

- Mean change in BCVA from baseline to month 24
- Mean change in BCVA from baseline to month 12
- Mean change in central retinal thickness from baseline to month 12 and month 24
- Number of injections from baseline to month 12 and 24

The additional secondary variables are:

- Mean change in area of new and existing geographic atrophy from baseline to month 12 and 24.

Patients at sites where autofluorescence can be undertaken will be assessed for the presence of geographic atrophy at Baseline, visit 4 (week 8) and then again at the 12 and 24 month visits. If present, the area of geographic atrophy will be estimated.

- New Geographic Atrophy at month 12 and month 24^a (Yes, No)
 - Change in area of geographic atrophy from the visit where geographic atrophy was first present
- Intra-retinal (IRF) and Sub-retinal fluid (SRF) (present/absent)

At each relevant assessment visit, the patient is examined for the presence/absence of IRF and SRF by the central reading centre as per the definitions for their treatment arm.

- The proportion of patients showing no IRF and SRF at month 2, 12 and 24
- Proportion of patients showing greater than or equal to 15 letters (EDTRS) gain and less than 15 letters loss from baseline to month 24.
- Proportion of patients with SRF as assessed by the [REDACTED] CRC and IRF as assessed by Investigators at baseline who do not resolve their SRF and IRF by Month 24

The remaining exploratory variables are:

- Proportion of patients with a) SRF, b) IRF, c) both SRF and IRF, d) neither SRF and/or IRF at baseline, month 2, 12 and 24
- Proportion of patients with $\geq 6/12$ visual acuity at baseline, month 12 and month 24
- Proportion of patients with 6/60 or worse visual acuity at baseline, month 12 and 24
- The proportion of patients with IRF and SRF at baseline who never resolve either their IRF or SRF at any visit up to Month 2, 12 and 24.
- Proportion of patients with SRF at baseline who never resolve their SRF at any visit up to Month 2, 12 and 24 (irrespective of their IRF)
- Proportion of patients with IRF at baseline who never resolve their IRF at any visit up to Month 2, 12 and 24 (irrespective of SRF)

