2.8.2.5 Mixed Modelling

The mixed models to be fitted are detailed in Table 2.8.2.5-1.

Table 2.8.2.5-1 Mixed Models

Model Number	Outcome Variable	Predictor/Covariate		Class Variable		Random Term
		Definite	Optional	Definite	Optional	
MM_1	Change in BCVA from baseline to 2, 12 and 24 months	
 • Treatment • Baseline BCVA • Visit (categorical) • Treatment by Visit Interaction 	
 • Stratification group • Cumulative weeks on treatment 	Treatment Visit Subject		Subject
MM_2	Change in BCVA from baseline to 2, 12 and 24 months	
 • Treatment • Baseline BCVA • Visit (categorical) • Treatment by Visit Interaction 	
 • Injection frequency • Cumulative number of weeks on treatment • Stratification group Baseline: 
 • Age • Lesion size • GA presence • Smoking status • Genotype saliva sample status • Baseline BCVA (<=70/>70) • Baseline IRF • IRF • Baseline SRF • SRF • PED • SRF resolved (y/n) 	Treatment Visit Subject	Stratum Centre	Subject
MM_3	Change in Geographic Atrophy from baseline to 2, 12 and 24 months.	
 • Treatment • Baseline GA area • Visit (categorical) • Treatment by Visit Interaction 	
 • Cumulative number of weeks on treatment Baseline: 
 • Age • BCVA • Injection frequency • Lesion size • GA presence • Smoking status • Genotype saliva sample status • Baseline BCVA (<=70/>70) • Baseline IRF • IRF • Baseline SRF • SRF • PED • SRF resolved (y/n) 	Treatment Visit Subject	Stratum Centre	Subject

Model Number	Outcome Variable	Predictor/Covariate		Class Variable		Random Term
		Definite	Optional	Definite	Optional	
MM_4	Change in CRT from baseline to 2, 12 and 24 months	
 • Treatment • Baseline CRT • Visit (categorical) • Treatment by Visit Interaction 	
 • Injection frequency • Cumulative number of weeks on treatment • Stratification group Baseline: Age 
 • Lesion size • GA presence • Smoking status • Genotype saliva sample status • Baseline BCVA (<=70/>70) • Baseline IRF • IRF • Baseline SRF • SRF • PED • SRF resolved (y/n) 	Treatment Visit Subject	Stratum Centre	Subject

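### Geographic atrophy area has two conflicting starting points and no stated value for absent atrophy, so new atrophy can fall partly or wholly outside the area endpoint

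*SAP*

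**What the plan says.** All of these are in the SAP unless stated.

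- Section 2.8.1 lists as an additional secondary variable "Mean change in area of new and existing geographic atrophy from baseline to month 12 and 24". On when an area exists it says: "If present, the area of geographic atrophy will be estimated". It then lists "New Geographic Atrophy at month 12 and month 24" as a yes/no variable, with change in area since first presence as a sub-item. That line carries a footnote marker whose text is not visible to us.
- Section 2.8.2, Table 2.8.2-2 has two GA rows. One is newly developed GA, analysed by logistic regression and survival analysis. The other is "Geographic Atrophy from Baseline to Month 12 / 24 (Change in area of geographic atrophy from the visit where geographic atrophy was first present", with the method given as "Mixed Modelling (Refer to Section 2.8.2.8". Section 2.8.2.8 covers logistic regression; the mixed models are in Section 2.8.2.5.
- Table 2.8.2.5-1 defines MM_3 with outcome "Change in Geographic Atrophy from baseline to 2, 12 and 24 months" and makes baseline GA area a definite covariate.
- The output shells (the Protocol document) follow MM_3: Table 14.2-18 summarises change from baseline in GA area, and Tables 14.2-21 and 14.2-22 model it.
- Section 2.4.1.1: where a treated patient's Visit 2 value is missing, "the baseline value for that patient will be imputed with" the Screening value. No other source is allowed.
- Section 2.4.1.2: post-baseline values are not imputed, and "Only subjects with measurements at any given time point will be included in the analysis for that given parameter and visit".

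**The concern.** The declared endpoint covers new as well as existing atrophy, so it has to respond when atrophy appears in an eye that had none. Two features of the plan work against this.

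First, the table that assigns methods to secondary endpoints starts the clock at first presence. The lesion's size when it first appears is then the reference value and is never counted as change.

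Second, no visible passage says whether an eye graded free of GA has an area of 0 mm² or no area. If it has none, MM_3 cannot use the eye, because both the covariate and the change are undefined.

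On that coding, the area result would describe growth only in eyes that already had GA, and a difference between the regimens in the appearance of new GA would not reach it. Two programmers could also follow the SAP faithfully and report different numbers for the same endpoint.

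**Working it through.** **1. The passages side by side**

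| Place | Starting point | Value when GA is absent |
|---|---|---|
| Section 2.8.1, declared variable | Baseline | Area estimated only if present |
| Table 2.8.2-2, area row | First visit with GA | Not needed |
| MM_3; shells 14.2-18, 14.2-21, 14.2-22 | Baseline | Needed, not stated |

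A Screening value does not help a GA-free eye, because the same conditional rule on area applies to it. New foci in an eye that already has GA are captured, because Listing 16.2.6-3 records the total area within the grid.

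**2. What each rule does to one eye** (assumed areas at baseline, Month 12 and Month 24)

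| Areas (mm²) | From baseline, absent = 0 | From first presence | From baseline, absent = missing |
|---|---|---|---|
| 0, 2, 3 | 3 − 0 = +3 | 3 − 2 = +1 | no value |
| 0, 0, 2 | 2 − 0 = +2 | 2 − 2 = 0 | no value |

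**3. The only GA area figures in the documents**

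Shell Table 14.1-10 prints GA absent in 291 of 347 eyes and definite in 56 (16.1%). Baseline area has n = 46 and 7, means 3.207 and 2.617, total mean 3.129, minimum 0.06.

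- Reproduced: (46 × 3.207 + 7 × 2.617)/53 = 3.129.
- Eyes without a baseline area if absent is missing: 347 − 53 = 294, which is 84.7%.
- Mean if the 291 absent eyes are set to 0: (53 × 3.129)/(53 + 291) = 0.482 mm².

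The printed n of 53 with a minimum above zero fits coding as missing. It does not prove it: the same numbers recur in Table 14.1-11 under genotype columns, so they look like example output. They serve for scale only.

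**4. Illustration of the area that would not enter MM_3 if absent is missing**

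Inputs: 165 eyes per arm (Section 2.12) and the shell share b = 56/347 = 0.161. This gives E = 165 × 0.161 = 26.6 eyes with GA and F = 138.4 without. Assumed: incidence p in GA-free eyes, and r = area of a new lesion at Month 24 divided by the two-year growth of an existing one.

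Share not counted = F·p·r / (E + F·p·r)

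| | r = 0.25 | r = 0.5 | r = 1 |
|---|---|---|---|
| p = 10% | 11.5% | 20.6% | 34.2% |
| p = 20% | 20.6% | 34.2% | 51.0% |

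Example: p = 10%, r = 0.5 gives 6.92/(26.6 + 6.92) = 20.6%.

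**5. Minor: who is at risk of new GA**

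LR_1 and shell Tables 14.2-23 and 14.2-20 (both on the Full Analysis Set) do not state the denominator. If eyes with baseline GA stay in as event-free, a true incidence of 20% reads 0.20 × (1 − 0.161) = 16.8%, and a true odds ratio of 2.25 (20% against 10%) reads 2.20. The effect on the comparison is slight.

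**The case against.** The strongest reply is that the from-baseline analysis exists. MM_3 and several shells specify it, and the Table 2.8.2-2 row itself opens with baseline to Months 12 and 24. For an eye with GA at baseline, first presence is baseline, so the two starting points agree there. New GA is analysed in its own right by logistic regression and survival analysis, and incidence plus growth is a legitimate two-part plan. An eye graded free of GA has been assessed, so treating it as unmeasured is a choice of reading. The footnote on new GA is not visible. Nor is the clinical study protocol that the SAP cites: the Protocol document supplied consists of output shells. Either could hold the rule.

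Most of this stands, and it limits the point. It does not remove it. The two starting points still differ for every eye with new GA. A two-part plan is not the single variable that Section 2.8.1 declares. The conditional wording on area, with the rule that only subjects with measurements enter, makes leaving absent GA missing the more natural result of following the text, and nothing visible says otherwise.

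The percentages in step 4 also restate assumed inputs and are not evidence. On the risk set, the reply largely succeeds: the wording already defines the event, and Table 14.2-23 displays baseline status.

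**Conclusion.** The point holds as a conflict of starting points together with a missing coding rule. Under the Table 2.8.2-2 row, the onset area of new GA is lost while later growth counts. Under MM_3, GA arising in an eye free of it at baseline stays out of the area endpoint if absent is left missing, and counts in full if absent is 0 mm².

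A reader might infer more than this, and the documents do not support it:

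- That the declared endpoint has no analysis. MM_3 and shells 14.2-18, 14.2-21 and 14.2-22 provide one.
- That new GA goes uncounted in the trial. LR_1 and the survival analysis count it as an event.
- That the shell figures establish coding as missing. They appear to be example output.
- That the optional GA presence covariate in MM_3 shows GA-free eyes were meant to enter. Nearly the same optional list stands under MM_2 and MM_4, so little can be drawn from it.

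The size is unknown. The range of 11% to 51% is an illustration that rests on an example prevalence, 10% to 20% incidence and relative lesion size of 0.25 to 1. The primary visual acuity endpoint is not affected. This is a cheap improvement to a secondary endpoint.

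**What to change.** 1. State the derivation: GA area is 0 mm² at any visit where the eye was assessed, is gradable and GA is absent; it is missing where the eye was not assessed or could not be graded.
2. In Table 2.8.2-2, add a row for change from baseline to Months 12 and 24 in area of new and existing GA, analysed by MM_3 in all eyes assessed and gradable at baseline, citing Section 2.8.2.5. Keep change since first presence as a separate supplementary variable and correct its cross-reference.
3. Minor: base LR_1, Table 14.2-23 and the GA survival table on eyes assessed and free of GA at baseline, and show the number at risk per arm. The optional baseline GA covariate in LR_1 is then constant and can go.

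The cost is wording in the SAP and shells plus one derivation rule, using data already collected. The drawback is that most changes will be exact zeros. With the step 4 inputs the share at Month 24 is (1 − 0.161) × (1 − p), or about 75% at p = 10% and 67% at p = 20%. The mean is then skewed, so use a robust standard error and report the number of eyes with GA beside it. A supportive rank test stratified by baseline GA is optional.

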2.8.2.1 Descriptive Summaries

All data will be listed.

All continuous data will be summarised by timepoint and treatment group using descriptive statistics. All categorical data will be summarized by timepoint (if appropriate) and treatment group by the number (and percentage) of patients in category.

For all patients, data will be recorded on scheduled visits for treatment. These visits are based on a bi-weekly visit grid, however each patient has their own set of scheduled visits which are determined by disease activity/visual impairment. Therefore, the number of visits differs between patients and as a consequence the number of available assessments/data at each visit differs. The time course of efficacy variable data will be presented/summarized as per the observed scheduled visits. As this differs between patients “by visit” tables presenting the overall time-course will be based on a biweekly time-grid.

Endpoints for BCVA improvement or BCVA loss will be summarized by presenting the number and percentage of patients in each treatment achieving the endpoint.

The mean BCVA value will be presented graphically by time point and treatment group, categorized by baseline BCVA value. The baseline categories will be: -0.29-0.00, 0.01-0.30, 0.31-0.60, 0.61-0.90, 0.91-1.20 and 1.21-1.50. The same graph will be presented for the mean BCVA change from baseline.

2.8.2.2 Supportive/Sensitivity Analyses

The primary endpoint will be assessed using a mixed model as described above with no imputation for missing data. Sensitivity analyses may include re-fitting the model with missing data imputed using the LOCF and multiple imputation (as detailed further in Section 2.8.2.3).

In addition, the primary model will be fitted to the Per-Protocol Set as a supporting analysis. Secondary and exploratory models may also be fitted to the Per-Protocol set as supporting or sensitivity analyses.

Secondary endpoints will be assessed with no imputation for missing data. Sensitivity analyses may be conducted; including the re-fitting of models with missing data imputed using the LOCF and multiple imputation, if appropriate. Furthermore, the secondary endpoint models may be fitted to use the Per-Protocol Set as supporting analyses.

Statistical models with optional variables may be explored to identify which model(s) optimally fit the data. In addition, ANCOVAs may be used to confirm cross-sectional analyses, as applicable.

Furthermore, one of the secondary outcomes is to explore the percentage of patients with > 15 letter improvement. This analysis provides a further supporting analysis of the primary endpoint.

2.8.2.3 Handling of missing values/discontinuations in efficacy analyses

For the primary analysis, there will be no imputation for missing data. The mixed model approach where all values recorded for each patient up to the time of withdrawal (or completion) are used is an appropriate model for data missing at random.

Sensitivity analyses will be conducted to explore the robustness of the data to the methods of dealing with missing data. These methods will include LOCF and multiple imputation.

2.8.2.4 Centre pooling

Not Applicable

2.8.2.5 Mixed Modelling

The mixed models to be fitted are detailed in Table 2.8.2.5-1.

Table 2.8.2.5-1 Mixed Models

Model Number	Outcome Variable	Predictor/Covariate		Class Variable		Random Term
		Definite	Optional	Definite	Optional	
MM_1	Change in BCVA from baseline to 2, 12 and 24 months	
 • Treatment • Baseline BCVA • Visit (categorical) • Treatment by Visit Interaction 	
 • Stratification group • Cumulative weeks on treatment 	Treatment Visit Subject		Subject
MM_2	Change in BCVA from baseline to 2, 12 and 24 months	
 • Treatment • Baseline BCVA • Visit (categorical) • Treatment by Visit Interaction 	
 • Injection frequency • Cumulative number of weeks on treatment • Stratification group Baseline: 
 • Age • Lesion size • GA presence • Smoking status • Genotype saliva sample status • Baseline BCVA (<=70/>70) • Baseline IRF • IRF • Baseline SRF • SRF • PED • SRF resolved (y/n) 	Treatment Visit Subject	Stratum Centre	Subject
MM_3	Change in Geographic Atrophy from baseline to 2, 12 and 24 months.	
 • Treatment • Baseline GA area • Visit (categorical) • Treatment by Visit Interaction 	
 • Cumulative number of weeks on treatment Baseline: 
 • Age • BCVA • Injection frequency • Lesion size • GA presence • Smoking status • Genotype saliva sample status • Baseline BCVA (<=70/>70) • Baseline IRF • IRF • Baseline SRF • SRF • PED • SRF resolved (y/n) 	Treatment Visit Subject	Stratum Centre	Subject

Model Number	Outcome Variable	Predictor/Covariate		Class Variable		Random Term
		Definite	Optional	Definite	Optional	
MM_4	Change in CRT from baseline to 2, 12 and 24 months	
 • Treatment • Baseline CRT • Visit (categorical) • Treatment by Visit Interaction 	
 • Injection frequency • Cumulative number of weeks on treatment • Stratification group Baseline: Age 
 • Lesion size • GA presence • Smoking status • Genotype saliva sample status • Baseline BCVA (<=70/>70) • Baseline IRF • IRF • Baseline SRF • SRF • PED • SRF resolved (y/n) 	Treatment Visit Subject	Stratum Centre	Subject

All results for all patients for will be included for each model, unless otherwise indicated. The repeated nature of the data will be modelled by including subject as random effect. The Kenward-Roger (KR) correction will be used to compute the denominator degrees of freedom to test fixed effects. The least square (LS) mean estimate for intensive retinal fluid treatment group (“intensive”) – relaxed retinal fluid treatment group (“relaxed”) will be obtained for treatment time = 2 months, 12 months and 24 months. These will be obtained with 95% confidence limits.

In regards to primary efficacy, if the upper 2-sided 95% confidence limit for the least square mean for intensive – relaxed mean change in BCVA at 24 months is <5 (the non-inferiority margin) then relaxed will be declared non-inferior to intensive.

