| Month 24, p-value                  |                             |          |        |         | x.xxxx            |                   |

\*Mixed Model: Change from Baseline (BCVA) = Baseline (BCVA) + Treatment + Visit (weeks) + Treatment \* Visit + Subject (random effect)  
CI: Confidence Interval;

**Note to Programmer:** The above table is an example only. Output to be updated to reflect aspects of the final model as appropriate.

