Table 2-1	Analysis set exclusion summary	8
Table 2.3-3	Study Assessment Windows	9
Table 2.7.2-1	Primary Efficacy Analyses.....	23
Table 2.7.2-2	Secondary Efficacy Analyses.....	23
Table 2.7.2-3	Exploratory Efficacy Analyses	23
Table 2.7.2.5-1	Mixed Models	26
Table 2.7.2.8-1	Logistic Regression Models.....	28

1 Introduction

[figure not shown]
Studies covered are listed in Table 1-1. The study design, objective, treatment duration, and efficacy variables for this indication may be different from other related studies due to different indications and phases of clinical development so that almost every study is unique. The main purpose is to provide project-level standards for the statistical analyses of efficacy and safety data which are common or similar across studies. This MAP can be used as a reference or guidance of statistical methods for future studies not listed in Table 1-1.

Table 1-1 Studies covered in the MAP

Indication /Study	Phase/ Duration	Treatment/ dose	Primary objective
AMD / RFB002	IV	(1) Intensive retinal fluid retreatment regimen (2) Relaxed retinal fluid retreatment regimen	To test the non-inferiority (visual acuity benefit that is not clinically worse) of intravitreal ranibizumab when administered to resolve IRF or SRF >200 µm under the fovea (relaxed retinal fluid management) relative to when administered to completely resolve both IRF and SRF (intensive retinal fluid management) in patients with wet AMD. The primary endpoint for the study will be the mean change in BCVA from baseline to month 24.

This is a randomised, multi-centre, non-inferiority trial investigating a relaxed fluid retreatment regimen relative to an intensive fluid retreatment regimen (using a non-inferiority margin of 5 letters on the primary endpoint of mean change in BCVA). After consenting to participate in the study, patients will participate in a screening period lasting up to 2 weeks to evaluate patient eligibility. After eligibility confirmation at the Baseline Visit, patients will be randomised in a 1:1 ratio to one of the two treatment arms i.e. intensive retinal fluid regimen or relaxed retinal fluid regimen within the appropriate stratum depending on the treatment at baseline for the non-study eye i.e. none, ranibizumab or other anti-VEGF therapy. Only one eye will be selected/treated as the study eye.

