2.1 General considerations

Descriptive statistics will include n (number of observations), mean, standard deviation, median, minimum and maximum for continuous variables, and frequencies and percentages for categorical variables.

The study eye is the eye identified by the investigator according to the protocol inclusion and exclusion criteria and recorded as such at the screening visit in the eCRF.

The efficacy analyses of this study will be based on the study eye data only.

For non-ocular, study eye, and fellow eye summary tables, figures, and listings will be based on all patients included in the analysis/set population under consideration. Unless otherwise specified, all confidence intervals (CIs) and p values will be two-sided and will be based on an alpha significance level of 0.05.

Central Reading Centre data will be used for efficacy summary tables and analyses, whilst all site and Central Reading Centre data will be included in listings.

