2.4.1.3 Visit Windows

Output presented by visit will use a derived visit number, based on the number of weeks from Day 1; the derived visit number will be calculated using the actual visit date, as opposed to the scheduled visit date. Listings will also include the CRF nominal visit.

Visit names available will be 4-weekly for the first 12 weeks, and then fortnightly. For example: Week 4, Week 8, Week 12, Week 14, Week 16, Week 18, etc., with each visit having a visit window of ± 7 days.

Month 12 and Month 24 visits will be analysed using the CRF nominal visit window.

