2.4.1.4 Early Discontinuation

The standard approach to handling Early Discontinuation visits will be to assign the visit to a derived visit number based on the date of termination. If the Early Discontinuation visit is assigned to a visit which already exists, then the assigned visit number will be set to the next visit.

Early Discontinuation visits may also be summarised as a separate distinct visit, in addition to, or in place of, the standard approach described in the paragraph above.

In addition, sensitivity analyses may be conducted to assess the impact of possible biases in endpoint analyses due to missing endpoint data for early withdrawal patients. These analyses may include Last Observation Carried Forward (LOCF), Baseline Observation Carried Forward (BOCF) and other imputation methods, as detailed further in Section 2.8.2.2.

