2.8 Efficacy evaluation

The primary objective is to evaluate the effectiveness of two treatment regimens by assessing the mean change in BCVA from baseline to Month 24 in each treatment group. A key secondary endpoint is to evaluate the effectiveness of two treatment regimens by assessing the mean change in BCVA from baseline to Month 12 in each treatment group. A mixed model (see below) utilising all data will be the primary analysis to assess both these endpoints in the one analysis with no imputation for missing data. Supportive and Sensitivity analyses will be conducted as described in Section 2.8.2.1.

Other key secondary variables include the central retina thickness and number of injections at Month 12 and Month 24.

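### The SAP does not fix which visits enter the primary BCVA model: the MM_1 row names Months 2, 12 and 24, while the text says all values up to withdrawal are used

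*SAP*

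**What the plan says.** **The model row.** SAP Table 2.8.2.5-1 gives the outcome of MM_1 and MM_2 as "Change in BCVA from baseline to 2, 12 and 24 months". Visit is categorical and a class variable, with a treatment-by-visit interaction and Subject as the random term.

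**The text.** SAP 2.8 says "A mixed model (see below) utilising all data will be the primary analysis". SAP 2.8.2.3 justifies the absence of imputation by a model in which "all values recorded for each patient up to the time of withdrawal (or completion) are used", and calls this suitable for data missing at random. The paragraph under the model table also says every patient's results go in, subject to a general exception for anything indicated otherwise. It then asks for least-squares means at 2, 12 and 24 months.

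**The output shell.** The footnote to Protocol Table 14.2-2 writes the model as "Baseline (BCVA) + Treatment + Visit (weeks"), plus the interaction and a random subject effect. Least-squares means are shown at Months 2, 12 and 24. The shell calls itself an example, to be updated to the final model.

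**Early discontinuation.** The standard rule in SAP 2.4.1.4 is to "assign the visit to a derived visit number based on the date of termination"; it also allows a separate visit as an addition or a replacement. SAP 2.4.1.3 puts derived visits on a four-weekly, then fortnightly grid, but says "Month 12 and Month 24 visits will be analysed using the CRF nominal visit window". SAP Table 2.4-3 puts Month 24 and early discontinuation in one column, at Week 104 with 14 days either side.

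**The concern.** Non-inferiority is decided from the Month 24 contrast of this one model, "using a non-inferiority margin of 5 letters on the primary endpoint of mean change in BCVA". Two programmers could follow the SAP faithfully and fit different data.

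Under the three-visit reading, a patient who loses vision and leaves at Month 20 contributes nothing after Month 12. The early-discontinuation BCVA usually lands on a fortnightly visit outside the model. A patient who enters the Full Analysis Set on a Week 4 BCVA alone contributes no row at all. A likelihood analysis corrects only for withdrawal that depends on what is in the model. If patients leave because of vision recorded between the modelled visits, that information is missing. If this happens more on the relaxed regimen, its Month 24 mean is overestimated. Intensive minus relaxed then shrinks, which favours declaring non-inferiority.

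Under the all-data reading, Visit has dozens of levels on a grid where attendance in a given week depends on disease activity (SAP 2.8.2.1), judged by arm-specific fluid criteria (Protocol Table 14.2-7). The only within-subject structure is a random intercept.

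**Working it through.** **1. The plan's own figure.** Inputs from SAP 2.12: margin 5, SD 15, true difference 0, 80% power, 15% dropout. SAP 2.1 says tests "will be two-sided and will be based on an alpha significance level of 0.05", so 0.025 one-sided.
- n = 2 × 15² × (1.960 + 0.842)² / 5² ≈ 141.3, so 142 per arm; 143 with the t distribution.
- 143 × 1.15 = 164.5, so 165. Division by 0.85 gives 169, within 3%.
- With 165 × 0.85 = 140.25 evaluable per arm, power is 79.4%.

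The stated 165 per group is reproduced and is not in question.

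**2. Size of the all-data grid.** Weeks 4, 8 and 12 are 3 visits. Weeks 14 to 104 in steps of 2 are (104 − 14)/2 + 1 = 46. Total 49 visits, or 98 visit-by-arm cells.

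**3. Bias in one arm's Month 24 mean.** Assumptions, none from the documents except the SD and the dropout total: 15 visits (Weeks 4, 8, 12, then 8-weekly to 100, and 104), SD 15, 15% dropout after Week 8. Dropout depends only on the last observed BCVA, with log-odds rising by the slope shown per SD of worse BCVA. Correlation is either constant at 0.7 or 0.4 + 0.5 exp(−weeks/40). There were 150,000 patients per scenario. Three visits means Weeks 8, 52 and 104; RI is random intercept, UN unstructured.

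| Correlation | Slope | Observed only | RI, 3 visits | UN, 3 visits | RI, 15 visits | UN, 15 visits |
|---|---|---|---|---|---|---|
| Constant | 0 | −0.06 | −0.05 | −0.05 | −0.05 | −0.05 |
| Constant | 0.5 | 0.78 | 0.12 | 0.12 | −0.04 | −0.04 |
| Constant | 1 | 1.54 | 0.30 | 0.31 | −0.01 | −0.01 |
| Constant | 2 | 2.46 | 0.53 | 0.58 | −0.02 | −0.03 |
| Decaying | 0 | 0.00 | 0.02 | 0.02 | 0.03 | 0.03 |
| Decaying | 0.5 | 0.74 | 0.25 | 0.29 | −0.04 | 0.04 |
| Decaying | 1 | 1.28 | 0.37 | 0.45 | −0.21 | −0.04 |
| Decaying | 2 | 2.09 | 0.71 | 0.89 | −0.26 | 0.01 |

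The zero-slope rows show simulation noise of about 0.05. The three-visit bias is about 0.1 to 0.9 letter under informative dropout. More visits remove it fully only with a suitable covariance.

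**4. Effect on the decision.** SE of the difference = 15 × √(2/140.25) = 1.79, ignoring any gain from baseline adjustment. If only the relaxed arm is affected, a bias of b letters gives one-sided error at the margin of Φ(−1.96 + b/1.79). For b = 0.1 this is about 3%; for b = 0.9, about 7%; the nominal value is 2.5%.

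**5. Heavier differential dropout.** Assumptions: random-walk covariance, SD 14.7, withdrawal about 7% intensive and 18% relaxed, log-odds rising 0.12 per letter lost in the relaxed arm only, true difference 4.90.
- Three visits, random intercept: 3.45, bias −1.45.
- Nine windows, random intercept: 3.89, bias −1.01. The windows alone remove 0.44/1.45 = 30% of the bias.
- Nine windows, unstructured: 4.87, bias −0.03.

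**6. Same mechanism in both arms.** In a separate simulation with 16% and 18% withdrawn, the three-visit contrast was biased by about −0.15, with Monte Carlo error near 0.08.

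**The case against.** The strongest reply is that the text already favours using everything. Three SAP statements point that way, and both the text under the model table and the shell list Months 2, 12 and 24 as times for least-squares means. The row may simply be naming reporting times. Nothing says interim or early-discontinuation BCVA is dropped. This stands as a possible reading. It does not settle the matter, because the row is headed as the outcome variable and the exception clause lets it restrict the data. A reader might infer from the row that these data are discarded; the documents do not establish that.

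A reader might also infer that the missing-at-random claim fails. That goes too far. A three-visit likelihood model is valid if withdrawal depends only on baseline and the modelled visits. Even in the scenarios above it removes most of the bias seen in observed means, for example 1.54 reduced to 0.30.

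Nor do the documents show that an early-discontinuation BCVA near Week 104 is lost. Table 2.4-3 pairs it with Month 24, while 2.4.1.3 and 2.4.1.4 suggest otherwise; the three places disagree.

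Finally, LOCF and multiple imputation are planned. SAP 2.8.2.3 says sensitivity analyses will be done, but 2.4.1.4 and 2.8.2.2 say only that they may be. The non-inferiority rule in any case uses the primary model alone.

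**Conclusion.** The point holds as an unresolved contradiction in the model that decides the trial. As written, the MM_1 row and the text describe different data, and no visit list settles which governs. On the literal row, the stated missing-data justification does not describe the fitted model, and protection is lost where withdrawal depends on vision between the modelled visits.

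The consequence for the Month 24 contrast is conditional:
- about nil if withdrawal is uninformative;
- small if the mechanism is the same in both arms with similar trajectories;
- roughly 0.1 to 0.9 letter toward non-inferiority if only the relaxed arm is affected, at about 15% dropout;
- about 1.5 letters in the heavier differential scenario.

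The correlation and dropout models behind these sizes are assumptions. The documents give no arm-specific withdrawal rates: SAP 2.12 plans 15% overall, citing 11% and 16% in two arms of an external trial. The all-data reading avoids most of this bias but, with a random intercept alone, was still off by up to about 0.3 letter in one arm's mean under decaying correlation. The 49-level grid itself was not simulated. The change should be made, since the choice otherwise rests with the analyst.

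**What to change.** - **Visits.** State that MM_1 uses the BCVA nearest to prespecified windows about 12 weeks apart, for example Weeks 8, 20, 32, 44, 52, 64, 76, 88 and 104, with Visit categorical and window boundaries given. SAP 2.6 lists intervals of 4 to 12 weeks, so an on-schedule patient in either arm has about one value per window.
- **Early discontinuation.** Place the BCVA in the window of its actual date, as Month 12 or Month 24 if within 14 days, and make Table 2.4-3, 2.4.1.3 and 2.4.1.4 agree.
- **Covariance.** Replace the random intercept alone with an unstructured within-subject covariance and a stated fallback for non-convergence. Without this the windows remove only part of the bias.
- **Reporting times.** State that Months 2, 12 and 24 are the times for least-squares means, and change the visit term in Protocol Tables 14.2-2 and 14.2-3 to categorical.
- **Sensitivity analyses.** Make 2.4.1.4, 2.8.2.2 and 2.8.2.3 agree on whether they are mandatory.

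The cost is SAP and shell wording, some programming, and more covariance parameters: 9 × 10/2 = 45, against 2 for a random intercept. The BCVA data are already collected. The Month 24 contrast, the 5-letter margin and the sample size stay as they are.
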